Collectively, the prior trials demonstrate the efficacy of RIC on an upper extremity for reducing myocardial infarction. The RIC stimulus varied with respect to the number of cycles used, as well as the remote location used. Concurrent medications including intravenous propofol⁽³⁹⁾ may have attenuated the cardioprotective effect of RIC. Although a mortality benefit was not observed, a minority of patients included in the meta-analysis had a large risk for RI as only 429 (23% of enrolled) patients had acute infarction, and the low risk of mortality in patients undergoing elective CABG, elective PCI or other surgical procedures in the meta-analysis limited detection of a mortality benefit with RIC. No patients with cardiac arrest were enrolled.

SAFETY

Application of medical devices (e.g. BP cuff) to the skin may be associated with adverse local effects such as pain or thrombophlebitis. Importantly, RIC is posited to modify the innate immune system, and so could contribute to infection or mask its diagnosis although no signal has been detected in the clinical trials of RIC. The safety of concurrent use of the autoRIC device in humans who may require defibrillation has not been evaluated.

RATIONALE FOR CURRENT PILOT STUDY

Both OHCA and STEMI share elements of RI with inflammatory changes that contribute to myocardial dysfunction and death,⁽⁹⁴⁾ and RIC may be beneficial in both indications: controlled studies in animal models as well as randomized trials in humans suggest that RIC attenuates RI and reduces infarct size in acute myocardial infarction, and controlled studies in animals suggest that RIC may be beneficial in cardiac arrest.

An automated device has been developed and can easily be applied to patients with OHCA to initiate RIC in the post-resuscitation period. However, the Food and Drug Administration (FDA) has not approved any device for RIC due to the absence of any controlled data demonstrating the benefit of RIC in humans with cardiac arrest. Our Institutional Review Board (IRB) has advised us that demonstration of the feasibility of randomization in the emergency department (ED) setting is necessary before proceeding to an assessment of its effectiveness in the out-of-hospital setting.

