Individual randomized trial with stratification by rhythm and permuted blocks of concealed size (Figure 2). To reduce potential bias due to using quasi-random methods or envelopes,^(98, 99) we will place sequentially numbered identically appearing active and sham RIC packages, which will be stored ready for use in a central location in the ED. When an eligible patient arrives in the ED, the medical assistant involved in their care will retrieve the next package and open it at the patient's bedside.

SETTING

Patients will be enrolled after transportation to Harborview Medical Center, Seattle, WA which annually receives a high-volume (≥ 50) of patients resuscitated from OHCA, is capable of performing PPCI 24 hours per day, seven days per week, and is staffed by investigators with a special interest in cardiac resuscitation.

[figure not shown]
POPULATION

Included will be those with:

- a) Age 18 years or more;
- b) Defibrillation by laypersons or defibrillation and/or chest compressions by EMS providers dispatched to the scene;
- c) Non-traumatic etiology of arrest, defined as without concomitant blunt, penetrating, or burn-related injury, or uncontrolled bleeding or exsanguination;

- d) Spontaneous circulation upon emergency department arrival;
- e) No response to verbal commands; and
- f) Ongoing or planned induced hypothermia.

FIGURE 2: DESIGN

Excluded will be those with:

- a) STEMI indicated on first 12-lead ECG obtained after restoration of circulation, defined as ST-elevation of ≥ 2 mm in two or more contiguous ECG leads;
- b) Written do not attempt resuscitation (DNAR) reported to providers before randomization;
- c) Drowning or hypothermia as cause of arrest;
- d) Known prisoner or pregnant; or
- e) Dialysis fistula in either upper extremity; or
- f) Pre-existing amputation of upper extremity.

STUDY TREATMENTS

Experimental Device

A standard non-invasive blood pressure cuff (e.g., American Diagnostics Corporation, Hauppauge, NY but any one can be used off the shelf) and disposable plastic clamp (e.g., Medline Industries Incorporated, Mundelein, IL) can be used to apply RIC in patients resuscitated from OHCA via three cycles of 5-mins. inflation to 200 mmHg followed by 5-mins. deflation of a blood pressure cuff on a thigh. The cuff occludes the artery; the clamp maintains pressure in the air bladder of the cuff during the inflation periods.

Control Group

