The control group will have a sham package opened at the bedside as soon as feasible after ED arrival. This will be identical in size, weight and appearance as that in the intervention group, but will contain a sham device. Upon identification that the patient has been randomized to the control group, the care team will proceed with all other resuscitative measures as in the the intervention group.

Initial critical care management of the post-cardiac arrest patient has a large influence on neurological recovery and survival.⁽¹⁰⁰⁻¹⁰⁴⁾ Combinations of hospital-based treatments improve outcomes in patients resuscitated from cardiac arrest compared to historical controls.⁽¹⁰⁵⁻¹¹⁰⁾ Moreover, patients transported to a receiving hospital with a coronary catheterization laboratory tended to have better outcomes versus transportation elsewhere.⁽¹¹¹⁾

Differences in initial care may explain some of the differences in survival rates for subjects admitted to different hospitals after resuscitation from cardiac arrest.⁽⁶⁾ Collectively, these studies demonstrate that hospital-based care of those resuscitated from OHCA impacts patient outcomes and potentially modifies the effect of interventions for cardiac arrest. Thus, experts have recommended a standardized approach to try to achieve optimal outcomes after resuscitation from cardiac arrest.⁽¹¹²⁾ According to this method, protocols for hypothermia-related care and other post-resuscitation care will be mandated via investigator agreements, as well as encouraged through periodic continuing education of hospital staff throughout the study period.

Standard post-resuscitation care will include early application and maintenance of IH followed by controlled rewarming, as is current practice at our institution. We will monitor adherence with IH in hospital, and require remediation if adherence does not meet *a priori* performance standards. Two trials that monitored treatment adherence observed improved outcomes with IH vs. no hypothermia after OHCA.^(29, 113) Earlier initiation of IH after hospital arrival is associated with significantly better survival.⁽¹¹⁴⁾ In contrast, IH without documented achievement of a therapeutic temperature range was not associated with benefit among patients resuscitated from in-hospital arrest.⁽¹¹⁵⁾ There is ongoing equipoise related to the duration and targeted temperature range of IH. In practice, most of our patients receive 24 h of IH targeted to 33°C.

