Survival to 30 Days After Cardiac Arrest assessed as alive 30 days after the index cardiac arrest as confirmed by a brief telephone interview. Note that some experts suggested that the primary outcome of trials in patients with OHCA should be assessed 90 days after discharge.⁽¹⁴¹⁾ However, we showed that such post-discharge scores were well correlated with assessments before discharge.⁽¹⁴²⁾ As well, post-discharge assessment was susceptible to informative missingness as the characteristics of those who consented for follow up were different from those who did not. Lyden and colleagues made similar observations about short vs. long-term outcomes after stroke.⁽¹⁴³⁾ Importantly, post discharge assessments burden patients and prolong study duration. We will confine post-discharge assessment to a brief telephone interview at 30 days.

Accrual is the proportion of eligible subjects who have the study device applied.

SAFETY OUTCOMES

Expected Adverse Events

Device Failure Malfunctions are unlikely due to the simple construction and durable materials of the devices. However, device failure will be defined as discontinuation of use of the device prior to the end of allocated treatment interval because of mechanical failure as opposed to provider preference.

Related to Device RIC is generally well-tolerated, but several side effects will be monitored. Most important are pain at the site of application, or thrombophlebitis, or infection.

Pain assessed using the Richmond Agitation-Sedation Scale at 30 and 60 minutes after randomization in control and intervention group patients.^(144, 145) No gold standard exists for pain assessment in sedated and ventilated patients.⁽¹⁴⁶⁾

Thrombophlebitis assessed as symptomatic non central nervous system venous or arterial thrombus documented radiographically or ultrasonographically.

Sepsis assessed within one week of index arrest as either i) the presence of microbiologically proven, clinically proven, or suspected infection; or ii) presence of Systemic Inflammatory Response Syndrome (SIRS); and iii) development of at least one organ dysfunction within the preceding 24 hours.⁽¹⁴⁷⁾

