ANALYSIS POPULATIONS

Safety Population

This will include all randomized patients, regardless of initial rhythm and duration of exposure to RIC. Patients will be analyzed within their assigned treatment arm, thereby using an intent-to-treat strategy. This is appropriate given that there are no controlled prior data related to RIC in patients with OHCA. Therefore, we are interested in testing the safety of RIC.

Efficacy Population

This will include all randomized patients whose initial rhythm was VF, regardless of duration of exposure to RIC. Patients will be analyzed within their assigned treatment arm, thereby using a modified intent-to-treat strategy. Note that rhythm is a pre-randomization variable.

SAMPLE SIZE

The null hypothesis is that the attrition rate will be not more than 25%. We assume 59 patients are treated by EMS providers for OHCA (21 due to VF) and have spontaneous circulation upon arrival at the participating receiving hospital annually. We will enroll 30 patients (15 per group) as recommended for pilot studies.⁽¹⁵²⁾ These numbers will allow estimation of accrual with precision (as measured by half-width of 95% CI) of at least 16.8% overall (and 23.7% within each group).

SAFETY AND DATA MONITORING PLAN

Clinical staff will report potential adverse events as soon as possible. The DSMB will review and approve the protocol before the study begins, evaluate rates of outcomes and adverse events throughout the study period, and determine the final monitoring plan. We will forward reports of DSMB recommendations to the FDA, Institutional Review Board (IRB), and sponsoring agencies as required by regulations for human subjects' research.

HUMAN SUBJECT ISSUES

Obtaining informed consent of patients resuscitated from OHCA, or from their legally authorized representative (LAR) is difficult. Patients are in an immediate life-threatening situation with a mortality rate before discharge of about 50%. Since study procedures must be initiated as soon as feasible after restoration of flow to ensure its efficacy,^(72, 153) we will seek approval from the FDA and IRB to conduct the study under exception from informed consent (EFIC) for emergency research.(CFR 50(24)) The initiation of study procedures prior to notification and consent will only apply to the application of the study device.

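### Thrombophlebitis counts only as a symptomatic, imaged thrombus, yet every patient is unresponsive at entry and *symptomatic* is not defined for such patients, so some cuff-limb events can go uncounted

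*Protocol*

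**What the plan says.** The protocol's Safety section names the harm as a local effect of the cuff: "Application of medical devices (e.g. BP cuff) to the skin may be associated with adverse local effects such as pain or thrombophlebitis". Under Safety Outcomes, Related to Device, it is one of three effects singled out: "Most important are pain at the site of application, or thrombophlebitis, or infection". The counting rule follows in the same subsection: "Thrombophlebitis assessed as symptomatic non central nervous system venous or arterial thrombus documented radiographically or ultrasonographically".

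The Population section requires all of its inclusion criteria to be met. Item (e) is "No response to verbal commands; and" and item (f) is "Ongoing or planned induced hypothermia". The Control Group section adds: "In practice, most of our patients receive 24 h of IH targeted to 33°C". Human Subject Issues gives the prognosis: "Patients are in an immediate life-threatening situation with a mortality rate before discharge of about 50" per cent.

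The pain item, directly before the thrombophlebitis item, acknowledges the difficulty of assessing these patients: "No gold standard exists for pain assessment in sedated and ventilated patients". The thrombophlebitis item makes no similar allowance. The protocol gives no definition of *symptomatic*, no limb examination and no scheduled limb imaging. Events are found through daily record review (Monitoring for Outcomes), reports by clinical staff (Safety and Data Monitoring Plan) and one telephone call at 30 days.

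**The concern.** A symptom requirement normally relies on the patient to complain or to respond to examination. Here no patient can do so at entry, most are then cooled for a day, and some die without waking. The condition is therefore poorly matched to the population, and the protocol leaves open whether a sign noticed by staff satisfies it.

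Two kinds of event can be lost, for different reasons. An imaged thrombus with no recorded symptom fails the symptom condition. Redness, swelling or a palpable cord that nobody images fails the thrombus-on-imaging condition, whatever *symptomatic* means.

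The stake is how a low or zero count will be read. Specific Aims gives confirmation of device safety for field use as one purpose of the study, and only 15 patients are to receive the cuff. A zero on this line could be taken as good local tolerability when it partly reflects what the definition admits.

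**Working it through.** **No plan figure to reproduce.** The protocol gives no expected rate or precision for this harm. Its only precision figures (16.8% overall, 23.7% per group) are not for this harm and play no part here.

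**Step 1: apply the rule as written to findings in the cuffed limb.**

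| Finding | Symptom condition | Thrombus on imaging | Counted? |
|---|---|---|---|
| Thrombus imaged after the patient wakes and complains | met | met | yes |
| Thrombus imaged after staff chart swelling in an unresponsive patient | undefined | met | depends on the abstractor |
| Thrombus seen on imaging done for another reason, no sign or complaint recorded | not met | met | no |
| Redness, swelling or cord charted, no imaging | arguably met | not met | no |

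Row 3 is lost through the symptom condition and row 4 through the imaging condition. Row 2 is an ambiguity.

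**Step 2: check the other routes.** Record review and staff reports may bring such a finding to light as a potential adverse event, but it still does not meet the defined outcome. The unexpected-event route would not ordinarily take it, because thrombophlebitis is already listed as expected.

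**Step 3: illustrate the size.** Let n = 15 (the planned intervention group), p = true thrombus rate and s = share of thrombi that qualify as symptomatic. Neither p nor s is in the documents; both are assumptions. Every qualifying thrombus is taken to be imaged.

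P(at least one counted) = 1 − (1 − p·s)^15

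| p | s = 1 | s = 0.75 | s = 0.5 | s = 0.25 |
|---|---|---|---|---|
| 5% | 53.7% | 43.6% | 31.6% | 17.2% |
| 10% | 79.4% | 68.9% | 53.7% | 31.6% |
| 20% | 96.5% | 91.3% | 79.4% | 53.7% |

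At p = 10%, expected counted events are 15 × 0.10 = 1.5 at s = 1 and 15 × 0.10 × 0.5 = 0.75 at s = 0.5.

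**Step 4: why the gap to s = 1 is an upper limit.** The s = 1 column assumes that every thrombus is imaged. Without screening, removing the symptom condition recovers only those symptom-free thrombi that happen to be imaged. If that share is r, the counted share becomes s + (1 − s)·r. At p = 10% and s = 0.5:

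- r = 0.1: counted share 0.55, 1 − 0.945^15 = 57%
- r = 0.2: counted share 0.60, 1 − 0.940^15 = 60%
- r = 0.5: counted share 0.75, 1 − 0.925^15 = 69%

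All are above 54% and below 79%.

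**Step 5: what a zero count would mean.** With 0 of 15, the one-sided 95% upper bound is 1 − 0.05^(1/15) = 18.1%. It applies to symptomatic, imaged thrombi only. Extending it to all thrombi would need a value of s that the protocol does not provide.

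**The case against.** The strongest reply is that *symptomatic* is undefined, not restricted to self-report. Swelling or discoloration noted by a nurse could qualify, and survivors who wake can complain. A reader might infer that unresponsive patients cannot be symptomatic and that the measure is therefore blind to harm. The text does not support that; what it supports is an undefined condition that is often hard to meet. This part of the reply stands.

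A reader might also infer from the stated mortality that half of all events are lost. That does not follow: death before discharge is not the same as never showing a limb sign, and some patients may wake before they die. Nor is the word *symptomatic* responsible for every loss, since phlebitis without imaging drops out because a thrombus must be shown.

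The protocol also says that outcomes are descriptive and that no claims will be made, and the rule is the same in both arms. So this is under-ascertainment of harm, not a biased test. The assumed rates of 5% to 20% have no support in the document, which reports no adverse events in the infarction trials it reviews.

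These points limit the size of the problem but do not remove it. An imaged cuffed-limb thrombus without a recorded symptom still scores zero, as does charted phlebitis without imaging. If staff-observed signs were meant to count, the protocol needs to say so.

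**Conclusion.** The definition is poorly matched to its population and should be amended. That rests on the wording alone: symptoms and an imaged thrombus are both required, every patient is unresponsive at entry, and no alternative criterion is given for patients who cannot report.

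The size of the undercount cannot be derived from the protocol. The fall from 79% to 54% in the chance of recording any event depends on an assumed 10% rate and an assumed half of thrombi qualifying. Even then it is an upper limit on what the wording change can recover. It should not be quoted as the expected loss. The point concerns how completely a named device harm is recorded. It does not affect the primary outcome or any planned comparison.

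**What to change.** Replace the single definition with two lines, both taken from the existing daily record review and neither needing screening imaging.

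1. **Thrombus.** Count any venous or arterial limb thrombus first documented after randomization on imaging ordered for any clinical reason. For each, record the site (cuffed limb or other), whether it was symptomatic or incidental, and whether a catheter was present.
2. **Local signs.** Count charted redness, swelling, discoloration or palpable cord, with or without imaging, in the limb used for the cuff. In controls, use the left arm, which the Intervention Group section names as the preferred cuff site.

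The control limb has to be stated because controls have no assigned cuff limb. The Experimental Device section describes a thigh cuff while the Intervention Group section describes the left upper arm. Those passages must be reconciled, and the control reference limb should follow the result.

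The cost is a change of wording and a few fields on the abstraction form. The downside is that some incidental or catheter-related thrombi will be counted. The site, symptom and catheter fields show these separately, which matters because 15 controls summarized descriptively give little help in interpreting them.

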Clinical research resources are limited. The effectiveness of interventions must be demonstrated definitively if claims of their health benefit are to have scientific credibility.⁽⁹⁵⁾ Since some experts endorse RIC,^(40, 96) while others question its merits,⁽⁹⁷⁾ we believe that a large trial of RIC after OHCA will inform future public policy. Planning a multi-center trial to evaluate the effectiveness of the intervention in this population is premature without preliminary evidence of its efficacy. The present study will assess the feasibility of applying the intervention early after restoration of circulation to justify the investment of limited resources in a large trial. To date, no trial has evaluated RIC in patients with cardiac arrest.

OTHER DESIGNS CONSIDERED

Note that RIC can be applied in the field or in the ED. But also note that electrocardiograms, defibrillators and fibrinolytic therapy were studied and used in the coronary care unit or ED before diffusing to the out-of-hospital setting. We believe that the feasibility of RIC needs to be demonstrated in the ED setting before this therapy diffuses to the out-of-hospital setting.

We previously conducted pilot studies that showed that IH by iced intravenous saline in patients resuscitated from OHCA was feasible either in hospital or in the field,^(1, 2) but the subsequent large trial showed that IH in the field was associated with an increased incidence of rearrest as well as pulmonary edema.⁽³⁾ Since implementation of RIC in the field may delay other important elements of care, and the benefit of RIC is unclear, we believe that demonstration of the feasibility of randomization in the emergency department (ED) setting is necessary before proceeding to an assessment of its effectiveness in the out-of-hospital setting.

PRELIMINARY EXPERIENCE WITH RIC IN PATIENTS WITH ACUTE CARDIOVASCULAR ILLNESS

We applied RIC to six patients resuscitated from OHCA or with presumed STEMI in our ED, using a manual cuff to inflate to 200 mmHg for five minutes then deflate for five minutes, clamp to reduce air leak during cuff inflation, and stopwatch to time each cycle. All patients underwent three cycles of cuff inflation-deflation. Two (33%) had air leak > 20 mmHg from the cuff, requiring manual reinflation during treatment. We have modified the use of the clamp to reduce air leak.

RESEARCH DESIGN AND METHODS

DESIGN

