The initial neurological⁽¹²²⁾ and cardiopulmonary status⁽¹²³⁾ upon hospital arrival are important determinants of outcomes after OHCA. Also, the initial degree of cardiopulmonary failure upon hospital arrival is predictive of subsequent development of multi-organ failure. Treating providers will be asked to document neurological status (assessed using the Full Outline of UnResponsiveness [FOUR] score)⁽¹²⁴⁾ and cardiopulmonary dysfunction (assessed using Serial Organ Failure [SOFA] score)⁽¹²⁵⁻¹²⁷⁾ before randomization. These scores are important covariates and will be useful for exploratory secondary analyses.

Documentation of Treatment

This will be assessed as treatment assigned; treatment received; time points used to monitor the time-dependent nature of the intervention including call to 911, sustained restoration of spontaneous circulation (ROSC), initiation of RIC, completion of treatment cycles.

Monitoring for Outcomes

Study staff will review subject's clinical record daily to monitor for outcomes and potential adverse events as well as to monitor use of concomitant treatments.

PRIMARY OUTCOME

Attrition assessed as the proportion of randomized subjects who do not remain on allocated therapy for the intended study duration among subjects randomly allocated. In the intervention group, this will be defined as lack of completion of three cycles of inflation-deflation; In the control group, this will be defined as crossover to the intervention group. Secondary and Exploratory Outcomes

Treatment Success assessed as the proportion of intervention group patients who remain alive and on their allocated therapy for the intended study duration.

Cardiac Function assessed as left ventricular ejection fraction (LVEF) using echocardiograms ordered for clinical indications.

Cardiogenic Shock assessed as systolic BP < 80 mmHg during any 6 h period within 48 h of the index arrest not due to a correctable cause, and treated with pressors or inotropes or placement of a mechanical cardiac assist device (e.g. intra-aortic balloon pump). Cardiogenic shock correlates with survival after resuscitation from cardiac arrest.^(21, 123)

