Related to Cardiac Arrest The following are commonly observed in patients who experience cardiac arrest, and may or may not be attributable to specific resuscitation therapies. These will be monitored and reported but not classified as serious adverse events. Clinical diagnoses of pneumonia, cerebral bleeding, stroke, seizures, bleeding requiring transfusion or surgical intervention, rearrest, pulmonary edema, serious rib fractures, sternal fractures, internal thoracic or abdominal injuries as noted in the hospital discharge summary.

Unexpected Adverse Events (UAE)

These will be defined as any serious unexpected adverse effect on health or safety or any unexpected life-threatening problem caused by, or associated with, a device, if that effect or problem was not previously identified in nature, severity, or degree of incidence in the investigation plan or application, or any other unexpected serious problem associated with a device that relates to the rights, safety or welfare of subjects. Death or neurological impairment will not be considered an adverse event in this study, as it is an expected part of the natural history of the illness for a large proportion of the population.

Covariates Key covariates of interest include but are not limited to:

Initial rhythm: (i) VF, vs. (ii) PEA, vs. (iii) asystole, vs. (iv) unknown.

Observational status of arrest:⁽¹⁴⁸⁾ (i) witnessed by EMS, vs. (ii) witnessed by bystanders, vs. (iii) unwitnessed;

Bystander CPR status:⁽¹⁴⁹⁾ (i) performed, vs. (ii) not performed, vs. (iii) unknown.

Response time interval from call to initiation of CPR by EMS:⁽¹⁵⁰⁾ among witnessed cardiac arrests grouped as (i) < 10 minutes, vs. (ii) ≥ 10 minutes.

Gender:⁽¹⁵¹⁾ (i) male vs. (ii) female.

Strata of initial depth of coma:⁽¹²⁴⁾ based on FOUR score.

Strata of initial cardiopulmonary dysfunction:⁽¹²⁵⁻¹²⁷⁾ based on SOFA score.

ANALYSES

Interim Analyses

The data will be monitored regularly by an independent data safety monitoring board (DSMB) to ensure study integrity and patient safety.

Monitoring of Study Conduct

The timeliness, completeness, and accuracy of data entry will be analyzed continuously, with reports provided monthly to the Study Executive Committee. This information will be provided in periodic reports to the DSMB.

Analyses

All outcomes will be summarized descriptively, without statistical comparison as recommended for pilot studies. No claims will be made based on the results of this trial.

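### Arrest-related safety events are defined from the discharge summary with no onset window, so events before randomization are not excluded, and the definition is not reconciled with the planned daily record review

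*Protocol*

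**What the plan says.** All references are to the protocol.

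- **Safety Outcomes, Related to Cardiac Arrest.** The list opens with "Clinical diagnoses of pneumonia, cerebral bleeding, stroke, seizures, bleeding requiring transfusion or surgical intervention" and closes with "rearrest, pulmonary edema, serious rib fractures, sternal fractures, internal thoracic or abdominal injuries as noted in the hospital discharge summary". It is one sentence, so the natural reading is that the source named at its end governs every event in it. Of these events the protocol says "These will be monitored and reported but not classified as serious adverse events". No onset time, window or reference to randomization is given.
- **Study Assessments, Monitoring for Outcomes.** "Study staff will review subject's clinical record daily to monitor for outcomes and potential adverse events".
- **Safety and Data Monitoring Plan.** "Clinical staff will report potential adverse events as soon as possible". The data safety monitoring board (DSMB) is to evaluate outcome and adverse event rates throughout the study.
- **Design and Population.** Entry requires defibrillation and/or chest compressions before hospital arrival. The package that reveals the allocation is opened at the bedside in the ED.
- **Documentation of Treatment.** The time points named are the 911 call, sustained return of circulation, start of conditioning and completion of cycles. Onset of safety events is not among them.
- **Other Designs Considered.** The group's earlier large trial of field hypothermia, which followed pilots that had shown feasibility, is described as "associated with an increased incidence of rearrest as well as pulmonary edema".

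**The concern.** The protocol has two accounts of how safety events are found, and it does not connect them. One is a daily look at the chart, which can date an event. The other is the discharge summary, which is written once, at the end of the stay. The definition of this event list rests on the second.

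Every patient has had an arrest and a field resuscitation before randomization, and several listed events are possible consequences of exactly that: rearrest, pulmonary edema, rib and sternal fractures, internal injuries. Without an onset rule, the count for each arm can mix what the patient arrived with and what happened after allocation. A short rearrest during the cuff cycles is counted only if the summary's author mentions it.

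At stake is the usefulness of the pilot's safety description. Specific Aims says that the study will confirm the safety of the device for field use and that its results will shape a future trial. The list includes the two events that appeared in the group's earlier field programme. The primary outcome, attrition, is not affected.

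**Working it through.** The protocol gives no figure for these events, so there is none to reproduce. The check is a comparison of the text, then a calculation of size.

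**Step 1: how other outcomes are anchored in time.**

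| Outcome | Section | Time anchor |
|---|---|---|
| Pain | Safety Outcomes | 30 and 60 minutes after randomization, both arms |
| Sepsis | Safety Outcomes | within one week of the index arrest |
| Cardiogenic shock | Secondary and Exploratory Outcomes | within 48 h of the index arrest |
| Rearrest, pulmonary edema and the rest of the list | Related to Cardiac Arrest | none; source is the discharge summary |

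The protocol sets windows elsewhere, so the gap is specific to this list.

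**Step 2: sequence of events for a patient.** Arrest, field compressions and/or defibrillation, return of circulation, transport, ED arrival, package opening (randomization), then conditioning or sham. A listed event in any step before package opening meets the definition as written if the summary mentions it.

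**Step 3: weight of one event.** Sample Size gives 30 patients, 15 per group.

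- One event: 1/15 = 6.7 percentage points in that arm.
- Two events: 2/15 = 13.3 percentage points.

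**Step 4: effect on a true difference (illustration, assumed inputs).** Let

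- q = risk of the event before randomization, the same in both arms;
- r = true risk after randomization;
- s = share of later events that reach the summary.

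If the two periods are independent and a patient counts once:

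observed risk = 1 − (1 − q)(1 − s·r)

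so observed difference = (1 − q)·s·(r₁ − r₀).

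Take r₀ = 10% and r₁ = 30%, a true difference of 20 points. The standard error (SE) is √[Σ p(1 − p)/15] over the two arms.

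| q | s | Observed risks | Difference | SE |
|---|---|---|---|---|
| 0 | 1 | 10% vs 30% | 20 points | 14 points |
| 0 | 0.7 | 7% vs 21% | 14 points | 12 points |
| 20% | 1 | 28% vs 44% | 16 points | 17 points |
| 20% | 0.7 | 25.6% vs 36.8% | 11.2 points | 17 points |
| 50% | 1 | 55% vs 65% | 10 points | 18 points |
| 50% | 0.5 | 52.5% vs 57.5% | 5 points | 18 points |

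Example for q = 20%, s = 1: 1 − 0.8 × 0.9 = 28%; 1 − 0.8 × 0.7 = 44%; SE = √[(0.28 × 0.72 + 0.44 × 0.56)/15] = √0.0299 = 17 points.

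Both mechanisms shrink a real difference by the factor (1 − q)·s. Counting earlier events also raises the noise. Neither creates a difference in expectation when r₁ = r₀.

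**The case against.** The strongest reply is that the sections can be read together: daily surveillance and prompt staff reports find events, and the summary only supplies the final classification. The protocol does say that these events will be monitored and reported. Moreover, the analysis is descriptive, no claims are to be made, the primary outcome is attrition, and an onset rule or time field often sits in the analysis plan or case report form, which are not shown. All of this limits the weight of the point. It does not remove it, because the source is fixed in the protocol itself and the protocol never states the combined reading.

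A reader might also infer stronger things that the documents do not support:

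- *That events before randomization will be counted.* The text only fails to exclude them.
- *That the summary omits brief events or carries no times.* Nothing describes what this hospital's summaries contain. Omission is a reasonable inference, no more.
- *That about 15 of the 30 patients have no usable source.* Human Subject Issues gives mortality before discharge of about 50%, and 0.5 × 30 = 15 is a count of deaths. The protocol is silent on what document is used for patients who die.
- *That the DSMB learns of these events only after discharge or death.* Daily review, prompt reporting and continuing DSMB evaluation are all planned.
- *That rearrest and pulmonary edema are suspected harms of conditioning.* They are cited as harms of field hypothermia, as a caution about moving a therapy into the field. The stated reasons for starting in the ED are possible delay to other care, unclear benefit and advice from the institutional review board. The device effects called most important are pain, thrombophlebitis and infection.
- *That the arms would be biased.* Randomization balances earlier events in expectation.

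A practical objection also stands: a rule that counts only events starting after package opening cannot be applied strictly to fractures and internal injuries when compressions came before arrival.

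**Conclusion.** The point holds in limited form. The definition uses the discharge summary without an onset window, is not reconciled with the daily review the protocol already plans, does not exclude events that precede randomization, and may miss brief later ones. Each such event is worth 6.7 points in an arm of 15.

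The consequence is dilution and noise. Under the assumed inputs, a true 20-point difference would appear as anything from 16 down to 5 points, with a standard error of about 17 to 18 points, once earlier events are mixed in. These figures rest on assumed risks, on independence of the two periods and on an assumed share of events reaching the summary. They show direction and scale, not a forecast.

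This should be corrected because a better source is already planned and the result is meant to inform a field trial. It does not threaten the primary outcome or the validity of the randomization.

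**What to change.** In Safety Outcomes, Related to Cardiac Arrest:

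1. Name the daily clinical-record review, including the ED and EMS records in the chart, as the source. Keep the discharge summary, or the death summary for patients who die, as a cross-check.
2. Record onset date and time for rearrest, pulmonary edema and other events that can be dated, and the package-opening time in both arms. Controls have no start of conditioning, so that time cannot serve as their clock. The pain assessment is already timed from randomization in both arms, so the reference time is needed anyway.
3. Report by arm the events that start after randomization, separately from those before it.
4. List fractures and internal injuries related to compressions as before randomization, after it, or of undeterminable onset.

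**Cost:** slightly more abstraction, one or two added time fields, and possibly higher counts of minor events. The daily review is already planned, and no treatment or patient procedure changes.
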